### 5.15.2. Special Safety Topics

#### 5.15.2.1. Hypoglycemic Episodes

Hypoglycemia will be classified as follows (ADA 2005):

- Documented Symptomatic Hypoglycemia: Any time a patient feels that he/she is experiencing symptoms and/or signs associated with hypoglycemia, and has a plasma glucose level of  $\leq 70$  mg/dL (3.9 mmol/L), or PG  $< 54$  mg/dL (3 mmol/L). Therefore, the category of interest will be:
  - Documented Symptomatic Hypoglycemia with PG  $\leq 70$  mg/dL
  - Documented Symptomatic Hypoglycemia with PG  $< 54$  mg/dL
- Asymptomatic Hypoglycemia: An event not accompanied by typical symptoms of hypoglycemia, but with measured plasma glucose of  $\leq 70$  mg/dL (3.9 mmol/L), or PG  $< 54$  mg/dL (3 mmol/L). Therefore, the category of interest will be:
  - Asymptomatic Hypoglycemia with PG  $\leq 70$  mg/dL
  - Asymptomatic Hypoglycemia with PG  $< 54$  mg/dL

- Severe Hypoglycemia: An episode requiring the assistance of another person to actively administer carbohydrate, glucagon, or other resuscitative actions. These episodes may be associated with sufficient neuroglycopenia to induce seizure or coma. Plasma glucose measurements may not be available during such an event, but neurological recovery attributable to the restoration of plasma glucose to normal is considered sufficient evidence that the event was induced by a low plasma glucose concentration. Severe hypoglycemia will be further divided in the following four subcategories:
  - Severe Hypoglycemia with PG  $\leq 70$  mg/dL
  - Severe Hypoglycemia with PG  $< 54$  mg/dL
  - Severe Hypoglycemia with PG  $> 70$  mg/dL
  - Severe Hypoglycemia with PG missing
- Nocturnal Hypoglycemia: Any hypoglycemic event that occurs between bedtime and waking. Therefore, the category of interest will be:
  - Nocturnal Hypoglycemia, events with PG  $\leq 70$  mg/dL included
  - Nocturnal Hypoglycemia, events with PG  $< 54$  mg/dL included
- Probable Symptomatic Hypoglycemia: An event during which symptoms of hypoglycemia are not accompanied by a plasma glucose determination (but that was presumably caused by a plasma glucose concentration of  $\leq 70$  mg/dL [3.9 mmol/L]), or PG  $< 54$  mg/dL (3 mmol/L). Therefore, the category of interest will be:
  - Probable Symptomatic Hypoglycemia, events with PG  $\leq 70$  mg/dL
  - Probable Symptomatic Hypoglycemia, events with PG  $< 54$  mg/dL

Cases of relative hypoglycemia will also be collected, but will not be included in the category of overall hypoglycemia:

- Relative Hypoglycemia: is defined as symptomatic events during which the person reports any of the typical symptoms of hypoglycemia, and interprets those as indicative of hypoglycemia, but with a measured plasma glucose concentration of  $> 70$  mg/dL (3.9 mmol/L). Therefore, the category of interest will be:
  - Probable Symptomatic Hypoglycemia, events with PG  $> 70$  mg/dL
  - Probable Symptomatic Hypoglycemia, events with PG  $\geq 54$  mg/dL

Total hypoglycemia includes any event that meets criteria for documented symptomatic hypoglycemia (including severe hypoglycemia), asymptomatic hypoglycemia, or probable symptomatic hypoglycemia. Those categories that are defined by PG will be analyzed by the PG  $\leq 70$  mg/dL threshold and by the PG  $< 54$  mg/dL threshold separately. Therefore, total hypoglycemia category will have the following two subcategories:

- Total Hypoglycemia (events with PG  $\leq 70$  mg/dL included)
- Total Hypoglycemia (events with PG  $< 54$  mg/dL included)

A listing of the individual hypoglycemic episodes, by patient, will be presented using all randomized population.

The incidence of hypoglycemic episodes will be summarized using frequency and percent. The frequency and percent at each visit are calculated as the number of patients and percent of patients reporting hypoglycemic episodes at that visit. The overall frequency and percent will also be reported. The overall frequency and percent are calculated as the total number of patients and percent of patients reporting hypoglycemic episodes during the entire study treatment period. The summary report will be conducted using ITT patients. Fisher's exact test or Chi-square test will be used for treatment comparison.

The hypoglycemia rates (episodes/patient/30 days, episodes/patient/year) for each visit, and overall will be analyzed using a negative binomial model with the generalized linear mixed model. The model will include treatment, country, SGLT2 inhibitor dose ("low" versus "high"), metformin use ("yes" versus "no"), visit, baseline HbA1c strata ( $\leq 8.0\%$  and  $> 8.0\%$ ) and treatment-by-visit interaction as fixed effect, and baseline hypoglycemia rate as a covariate. For the above mentioned analysis, PROC GLIMMIX in SAS will be used with random statement. The logarithm of days between visits will be adjusted as an offset to account for possible unequal duration between visits and between patients. The predicted hypoglycemia rate per 30 days and per year by treatment and visit will also be presented. An unstructured covariance structure will be used to model the within-patient errors. If this analysis fails to converge, the following covariance structures will be tested in this order: compound symmetry, then, autoregressive.

Additional exploratory analyses may be performed if deemed necessary.

#### **5.15.2.2. Percentage of Patients Receiving Rescue Medication due to Severe, Persistent Hyperglycemia**

Frequency counts and percentage of patients receiving rescue medication due to severe persistent hyperglycemia will be presented using ITT population. Fisher's exact test will be applied to compare treatments on the proportion of patients receiving rescue medication due to severe persistent hyperglycemia. Time to receiving rescue medication due to severe persistent hyperglycemia will be analyzed to compare treatment groups using a semi-parametric proportional hazard Cox regression model with treatment, country, SGLT2 inhibitor dose ("low" versus "high"), metformin use ("yes" versus "no"), baseline HbA1c strata ( $\leq 8.0\%$  and  $> 8.0\%$ ) as fixed effects, and baseline HbA1c as a covariate. A Kaplan-Meier curve will be plotted for both treatments on the same graph, for presentation purposes. These same reports will be also provided for patients meeting criteria for severe persistent hyperglycemia, irrespective of whether they received rescue therapy while in the trial or not.

#### **5.15.2.3. Pancreas Safety**

Listing and summary will be provided for all events that submitted for adjudication. Listing and summary of adjudicated pancreatic events will also be provided.

#### **5.15.2.4. Cardiovascular Safety**

Listing and summary of events submitted for adjudication will be provided. Listing and summary of adjudicated cardiovascular (CV) events will also be provided. Heart rate and

systolic and diastolic blood pressure from vital signs will be summarized as well as ECG data (see Section 5.15.2.4.1 and Section 5.15.2.4.2 for details). In addition to the summary of AEs from the CV SOC, an additional summary of AEs suggestive of hypotension will be provided.

#### **51524.1. Vital Signs**

All vital signs will be listed using the all randomized population. The average value (mean of two measurements) will also be listed.

The measurements will be averaged for each patient at each visit. The average values will be used in the descriptive summaries and analyses.

Descriptive statistics for the change from baseline for sitting systolic, diastolic blood pressures and heart rates (HR) will be presented and will be analyzed using an MMRM model described in Section 5.2. Summaries and analyses will be conducted using the ITT population. The selection of the variance-covariance structure is discussed in Section 5.2. There will be no multiplicity adjustments for analyses of vital signs. Corresponding figures will be presented.

#### **51524.2 Electrocardiogram**

A listing of the individual and averaged ECG measurements (Heart Rate, QT, RR, QRS, PR and corrected QTs [QTc]) by patient will be produced using the all randomized patient population. Also, a listing of abnormal selected ECG parameters by patient will be produced using the all randomized patients population.

Descriptive statistics for the actual measurements and change from baseline, by treatment arm and visit, for selected ECG parameters will be presented using ITT population. The parameters that are included in the summary and analysis with an ANCOVA model are ECG heart rate and the QT, QTcF, QTcB, RR, PR, and QRS intervals.

The ANCOVA approach suggested by Dmitrienko and Smith (2002, 2003) will be the primary method of correcting QT interval for RR interval.

A mixed-effect ANCOVA model for QT change from baseline with the RR change from baseline and baseline QT as covariates will be used where treatment, country, SGLT2 inhibitor dose (“low” versus “high”), metformin use (“yes” versus “no”), baseline HbA1c strata ( $\leq 8.0\%$  and  $> 8.0\%$ ) as fixed effect, and patient will be the random effect. Least-squares mean obtained from this model by primary treatment group and visit, along with the standard error (SE) of the LS mean for the change from baseline measurements will be displayed. Treatment comparisons will be displayed, showing the treatment difference LS mean and the 95% CI of the treatment difference along with the p-value for treatment comparison.

Additional correction methods such as Fridericia’s and Bazett’s corrections will also be used to correct the QT interval.

For quantitative ECG variables, summaries and analysis of treatment emergent abnormal values will also be provided.

Selected thresholds for HR, PR interval, and QTc interval shown in the following [Table GBGE.5.2](#) will be used to summarize clinically relevant abnormal values for these variables.

Redacted Version

**Table GBGE.5.2. Thresholds for HR, PR, and QTc Interval**

ECG Variable (unit)	Threshold
QTcF actual measurement (msec)	>450 for males, >470 for females > 480, >500
QTcF Change from Baseline (msec)	>60, >30, <-60, <-30
ECG heart rate (bpm)	>=130, >100, <50 >100 and increase from baseline >=15 <50 and decrease from baseline <= -15
PR interval (msec)	≥220 ≥220 and increase >20 ≥220 and increase >40 ≥220 and 0 < Increase <= 25% from baseline ≥220 and Increase > 25% from baseline

Abbreviations: bpm = beats per minute; ECG = electrocardiogram; HR = heart rate; PR = pulse rate.

For qualitative ECG outcomes, treatment-emergent abnormalities will be summarized and compared using the likelihood-ratio test. Abnormalities will also be grouped hierarchically into categories. The top level categories include rhythm, conduction, axis, morphology, ischemia, infarction, injury, ST segment, T wave, U wave and other. Percent of patients in each category will be compared using Pearson chi-square test. Other qualitative analyses may be conducted, if deemed necessary.

#### 5.15.2.5. Thyroid Safety

Listings of AEs of interest associated with the thyroid gland (benign and malignant neoplasms) will be produced, as well as a listing of biopsy reports. For calcitonin, summaries and analysis for changes from baseline and treatment emergent abnormal values will be provided as well as listing of abnormal values. Shift tables may be provided if appropriate.

#### 5.15.2.6. Renal Safety

To assess renal safety, summary and analyses for changes from baseline will be provided for estimated glomerular filtration rate (eGFR), as well as shift tables. Treatment emergent abnormal values will be summarized and analyzed. Listing of AEs suggestive of acute and chronic kidney failure will also be provided. Other reports may also be generated if deemed appropriate.

#### 5.15.2.7. Allergic/Hypersensitivity Reactions

Listing and summary of allergic and other hypersensitivity AEs will be provided.

### 5.15.3. Analysis of Laboratory Analyte

All laboratory measurements including scheduled and unscheduled will be listed by patient by visit using all randomized patients. An additional listing will be presented for all laboratory

measurements that are outside the normal range. Certain laboratory measurements will be listed using clinical relevant thresholds other than laboratory limits.

All summary analyses will be conducted by treatment group using ITT population.

Descriptive statistics will be presented, by treatment group and visit, for the laboratory measurements. For each continuous laboratory measurement, the change from baseline, at each visit, will be analyzed using ANOVA on the ranks, with treatment as a fixed effect. Last-observation-carried-forward will be used to impute missing post baseline values for the last visit. Continuous lab measures will also be compared to reference range to determine whether they are abnormally high, low or normal. The incidence and percent of high, low and normal values will be listed for each of the treatment arms and compared using the Fisher's exact test or Chi-square test. Shift table will also be presented for each continuous measure.

For subjective (qualitative) laboratory assessments, count and percent of normal and abnormal values will be analyzed using Fisher's exact test or Chi-square test.

Counts and percentages for patients with pancreatic enzymes above upper limit of normal (ULN) and greater than or equal to  $3 \times \text{ULN}$  will be summarized at baseline and by visit for each treatment group.

A summary of changes (shift tables using normal and abnormal categories) in amylase (total, pancreatic) and lipase evaluation from baseline to the maximum postbaseline will be produced.

Additional analyses will be conducted if deemed necessary.

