**Table GBGE.4.1. Objectives and Endpoints**

Objectives	Endpoints

Primary To demonstrate that once-weekly dulaglutide (1.5 mg and/or 0.75 mg) is superior to placebo as measured by HbA1c at 24 weeks (change from baseline) in patients with inadequately controlled T2D on concomitant SGLT2 inhibitor therapy.
	
 
• The change in HbA1c from baseline to 24 weeks
 

Secondary Key secondary efficacy objectives (controlled for type 1 error) are to compare dulaglutide 1.5 mg and 0.75 mg to placebo at 24 weeks
 
Other secondary efficacy objectives are to compare dulaglutide 1.5 mg and 0.75 mg to placebo at 24 weeks
 
Secondary safety objectives are to compare dulaglutide 1.5 mg and 0.75 mg to placebo at 24 weeks
	
 
• Proportion of patients with HbA1c target values of <7.0% at 24 weeks
 
• The change in FBG (central laboratory) from baseline to 24 weeks
 
• The change in body weight from baseline to 24 weeks
 
 
 
• Proportion of patients with HbA1c target values of ≤6.5% at 24 weeks
 
• The change in 6-point SMPG profile from baseline to 24 weeks
 
• The change in fasting glucagon from baseline to 24 weeks
 
 
Incidence of:
 
 
• Treatment-emergent adverse events (TEAEs)
 
• Early discontinuations due to AEs
 
• Adjudicated cardiovascular and pancreatic AEs
 
• Thyroid neoplasms AEs
 
• AEs related to kidney failure, eGFR
 
• Systemic hypersensitivity AEs
 
• Local injection site reactions
 
• The change in systolic and diastolic blood pressure, heart rate, and lipids from baseline to 24 weeks
 
• Incidence and rate of hypoglycemic episodes
 
• Ketoacidosis, and initiation of rescue therapy for severe persistent hyperglycemia
 

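### Laboratory changes, including lipids, are tested by rank ANOVA with treatment only; adding ranked baseline as a covariate would gain precision at almost no cost

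*SAP*

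**What the plan says.** Section 5.15.3 sets one rule for every continuous laboratory measure: at every visit, its change from baseline "will be analyzed using ANOVA on the ranks, with treatment as a fixed effect". For missing data it adds: "Last-observation-carried-forward will be used to impute missing post baseline values for the last visit". The same section also provides categorical checks: "Continuous lab measures will also be compared to reference range to determine whether they are abnormally high, low or normal". Shift tables and counts of raised pancreatic enzymes follow.

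Table GBGE.4.1 lists as a secondary safety endpoint: "The change in systolic and diastolic blood pressure, heart rate, and lipids from baseline to 24 weeks". Lipids have no model elsewhere in the SAP, so the general laboratory rule applies to them. Blood pressure and heart rate, from the same bullet, are treated differently: under Vital Signs their change "will be analyzed using an MMRM model described in Section 5.2".

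For kidney function, section 5.15.2.6 says that "summary and analyses for changes from baseline will be provided for estimated glomerular filtration rate (eGFR), as well as shift tables", without naming a model. Section 5.15.2.5 does the same for calcitonin.

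**The concern.** Most change-from-baseline models that the SAP writes out in full include the endpoint's own baseline as a covariate: HbA1c (5.11), body weight (5.12.1), fasting glucose (5.12.2), fasting glucagon (5.13.1), SMPG (5.13.3) and QT (Electrocardiogram section). Fasting glucose and glucagon are themselves laboratory analytes. The general laboratory rule departs from this practice, and the SAP gives no reason.

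Subtracting baseline is not the same as adjusting for it. A change score fixes the slope on baseline at 1. When the correlation between baseline and follow-up is below 1, that over-corrects, and the change stays negatively related to baseline. This has two consequences. The comparison carries avoidable noise, so a real difference in lipids is somewhat more likely to be missed. And when the arms differ at baseline by chance, regression to the mean pushes the changes apart without any drug effect.

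**Working it through.** **The plan's own figure.** The only power statement is for HbA1c (section 5.1): difference 0.55, SD 1.2, two-sided alpha 0.025, power 90%. Then n = 2 × (2.241 + 1.282)² × 1.2² / 0.55² = 118.2, so 119 per arm against the stated 120. Enrolment is 120 / 0.85 = 141.2, so 142 per arm and 426 in total. These figures reproduce. They say nothing about laboratory precision; only the 142 per arm is used below.

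**Inputs for the check.** Two-sided alpha is 0.05 (the default in section 5.2). The baseline-to-endpoint correlation ρ is not in the SAP and is assumed to lie between 0.5 and 0.9. Baseline and follow-up variances are taken as equal.

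**Raw-scale formula.** With common variance σ², the change score has variance 2σ²(1 − ρ) and the baseline-adjusted response has σ²(1 − ρ²). The ratio, adjusted to unadjusted, is (1 + ρ)/2. If the unadjusted test has 80% power, the adjusted one has Φ(2.802/√ratio − 1.960).

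| ρ | Variance ratio | Excess SE of change score | Adjusted power when unadjusted is 80% |
|---|---|---|---|
| 0.5 | 0.75 | 15% | 90% |
| 0.7 | 0.85 | 8% | 86% |
| 0.9 | 0.95 | 3% | 82% |

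**Rank scale, as planned.** The SAP's test uses ranks, so the raw-scale figures are only a guide. Simulation: 3 arms × 142, 3,000 trials per setting, complete data, rank of change on treatment, without and with rank of baseline. The effect was set to give 80% power to the raw change score: 2.802 × √(2(1 − ρ)) × √(2/142), which is 0.33 SD at ρ = 0.5. Log-normal data used a log-scale SD of 0.5.

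| Data | ρ | Power without baseline | Power with baseline |
|---|---|---|---|
| Normal | 0.5 | 78.5% | 88.0% |
| Normal | 0.7 | 76.8% | 82.1% |
| Normal | 0.9 | 77.9% | 80.3% |
| Log-normal | 0.5 | 78.6% | 86.5% |
| Log-normal | 0.7 | 76.7% | 81.4% |
| Log-normal | 0.9 | 75.7% | 77.1% |

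Allowing for variation between repeated simulations, the gain is about 7 to 10 points at ρ = 0.5, 3 to 6 at 0.7 and 1 to 2 at 0.9. With no treatment effect, both methods rejected in 4.4% to 5.2% of trials.

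**Chance imbalance.** Suppose there is no drug effect and the two arms' baselines differ by 2 standard errors. On the normal scale the unadjusted test statistic then has mean of size 2√((1 − ρ)/2) and SD √((1 + ρ)/2).

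- ρ = 0.5: mean 1.00, SD 0.866, false-positive rate 13%.
- ρ = 0.7: mean 0.775, SD 0.922, false-positive rate 10%.
- ρ = 0.9: mean 0.447, SD 0.975, false-positive rate 7%.

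In simulated log-normal trials with an imbalance of at least 1.8 standard errors, the planned rank test gave about 11% to 15% at ρ = 0.5 and 0.7, and 7% at 0.9. With ranked baseline in the model, the rate was about 4% to 6%.

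**The case against.** The strongest reply is that nothing here is wrong. The test is pre-specified and keeps its error rate, and ranks are a sensible single rule for many analytes, some of them skewed. Laboratory safety also rests on abnormal-value incidence, shift tables and enzyme threshold counts. All of that stands. The categorical summaries detect range crossings, however. They do not replace the comparison of change, which is the listed lipid endpoint.

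A second reply is that the SAP does not always adjust for continuous baseline: the subgroup model by HbA1c stratum in section 5.16 leaves it out. That is so, but the stratum itself carries baseline in two levels. The vital-signs model does not have its terms listed, so it shows only a different method, not an explicit baseline term.

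Third, the size depends on an undocumented correlation and an assumed effect. That also stands; for very stable analytes the gain is slight.

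Fourth, rank ANCOVA assumes roughly linear, parallel relationships between ranks. In the simulations this did no visible harm to the error rate, including with log-normal data. Neither method estimates a difference in clinical units.

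A reader might go further and infer that baseline is ignored, that the SAP states rank ANOVA for eGFR and calcitonin, or that the laboratory tests are invalid. The SAP supports none of these. The response is already a change from baseline. For eGFR and calcitonin the method is only inferred from the general rule. And the type I error, averaged over chance imbalances, is nominal.

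**Conclusion.** This is a worthwhile improvement and does not correct an error. Section 5.15.3 gives up precision that the baseline values already collected would supply, most clearly for lipids. The cost is about 7 to 10 power points at a correlation of 0.5, 3 to 6 at 0.7 and 1 to 2 at 0.9. Protection against a chance baseline imbalance is also lost. These sizes assume 142 patients per arm with complete data, equal variances at both times, and an effect for which the unadjusted raw-scale test would have 80% power. No laboratory test is among H1 to H8 in section 5.3, so the primary and key secondary conclusions are untouched.

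**What to change.** In section 5.15.3, replace the rank ANOVA with a rank ANCOVA that regresses the rank of the change on treatment and the rank of the baseline value, with no optional terms left open. State there that it applies to lipids, and refer to it from sections 5.15.2.5 (calcitonin) and 5.15.2.6 (eGFR) so that their method no longer has to be inferred. The categorical summaries and shift tables stay as they are.

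The cost is a sentence or two in the SAP and one covariate in an existing program. No new data and no change in sample size are needed.

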### 5.16. Subgroup Analyses

Population subgroups of interest will be analyzed for the variables of HbA1c and body weight. Other variables may also be evaluated.

The following are candidate subgroups that might be analyzed. This list is not necessarily all-inclusive:

- baseline age group (<65 years,  $\geq 65$  years)
- race
- ethnicity
- country
- duration of diabetes at baseline (<median duration and  $\geq$ median duration)
- BMI (<median and  $\geq$ median)
- concomitant metformin
- baseline HbA1c ( $\leq 8.0\%$  and  $> 8.0\%$ )
- baseline glucagon (<median and  $\geq$ median)

An analysis will be performed examining the treatment-by-subgroup interaction term at Week 24 using the MMRM model with country, treatment, SGLT2 inhibitor dose (“low” versus “high”), metformin use (“yes” versus “no”), visit, subgroup, subgroup-by-treatment interaction, treatment-by-visit interaction, subgroup-by-visit interaction, and subgroup-by-treatment-by-visit interaction as fixed effects and baseline (HbA1c or body weight) as a covariate. For the subgroup analysis of baseline HbA1c strata ( $\leq 8.0\%$  and  $> 8.0\%$ ), the model will include country, treatment, SGLT2 inhibitor dose (“low” versus “high”), metformin use (“yes” versus “no”), visit, subgroup, subgroup-by-treatment interaction, treatment-by-visit interaction, subgroup-by-visit interaction, and subgroup-by-treatment-by-visit interaction as fixed effects. Baseline HbA1c will not be included as a covariate. The interaction effects at Week 24 will be evaluated using a significance level of 0.10, unadjusted.

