## 5. A Priori Statistical Methods

### 5.1. Determination of Sample Size

With 120 completers per arm, the study will have 90% power for demonstrating superiority of either dulaglutide 1.5 mg or 0.75 mg versus placebo in change from baseline in mean hemoglobin A1c (HbA1c) at 24 weeks, assuming a standard deviation (SD) of 1.2%, a difference between dulaglutide and placebo of 0.55%, and a 2-sided significance level of 0.025. Assuming that the dropout rate is 15% for the entire study period, the study will need to enroll at least approximately 142 patients in each arm for a total of 426 patients enrolled. Assuming a screen fail rate of 40%, a total of approximately 710 patients will be screened to meet these enrollment number requirements.

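### SAP Section 5.16: as written, the baseline HbA1c subgroup model analyses body weight without baseline weight as a covariate

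*SAP*

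**What the plan says.** Section 5.16 (Subgroup Analyses) names HbA1c and body weight as the variables to be analysed by subgroup and gives two MMRM specifications.

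- **General subgroup model.** Its list of terms ends: "subgroup-by-treatment-by-visit interaction as fixed effects and baseline (HbA1c or body weight) as a covariate". The covariate therefore follows the outcome.
- **Model for the baseline HbA1c strata (≤8.0%, >8.0%).** It has the same factors and interactions but only fixed effects. No continuous covariate is listed, and the next sentence reads: "Baseline HbA1c will not be included as a covariate". Neither the model nor this sentence is restricted to the HbA1c outcome.

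The subgroups are described as candidates that may or may not be analysed. Interactions at Week 24 are tested at 0.10 without adjustment. The SAP states no power for any interaction.

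**The concern.** The exclusion sentence makes sense when the outcome is change in HbA1c, because the subgroup factor is cut from baseline HbA1c. It gives no reason to leave baseline weight out of an analysis of weight change, since baseline weight does not define the stratum. Yet the model that must serve both outcomes lists neither baseline.

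Two programmers could therefore build different weight models from the same text. If the literal one is built, the within-stratum effects and the treatment-by-stratum interaction for weight are estimated with more residual variance than necessary. They also come from a model that departs, without explanation, from the SAP's main weight model. For HbA1c there is a lesser question: whether the two-level stratum is an adequate substitute for the continuous baseline.

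**Working it through.** **1. The models side by side**

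| SAP section | Stratum or subgroup term | Continuous baseline covariate |
|---|---|---|
| 5.16, general subgroup model | subgroup and its interactions | baseline of the outcome (HbA1c or weight) |
| 5.16, HbA1c-stratum model | stratum and its interactions | none named; baseline HbA1c excluded |
| 5.12.1, main weight MMRM | HbA1c stratum | baseline body weight |
| 5.15.2.2, Cox model for rescue | HbA1c stratum | baseline HbA1c |

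Section 5.12.1 shows that the stratum and baseline weight are meant to sit together. Section 5.15.2.2 shows that the SAP does not treat the stratum and continuous baseline HbA1c as mutually exclusive.

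**2. Body weight: cost of omitting baseline weight**

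Let r be the correlation between baseline weight and weight change, given the other model terms. The SAP does not state r, so 0.1 to 0.3 is assumed. The ratio of the standard error without the covariate to that with it is 1/√(1 − r²).

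- r = 0.1: 1/√0.99 = 1.005 (+0.5%)
- r = 0.2: 1/√0.96 = 1.021 (+2.1%)
- r = 0.3: 1/√0.91 = 1.048 (+4.8%)

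**3. HbA1c: reproduce the plan's own figure first**

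Inputs from Section 5.1: "With 120 completers per arm, the study will have 90% power", "assuming a standard deviation (SD) of 1.2" (in percentage points), "a difference between dulaglutide and placebo of 0.55", and "a 2-sided significance level of 0.025".

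- SE of the difference = 1.2 × √(2/120) = 0.155, and 0.55/0.155 = 3.55.
- Power = Φ(3.55 − 2.24) = 90.5% (90.1% with the noncentral t).
- With 15% dropout, 120/0.85 = 141.2, rounded up to 142 per arm; 3 × 142 = 426.

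The stated sample size reproduces.

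**4. Interaction power for HbA1c, one dose against placebo**

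Let s be the share of patients at or below 8.0% (assumed). SE = 1.2 × √(2/(120s) + 2/(120(1 − s))), with a two-sided test at 0.10. At s = 0.5, SE = 1.2 × √(4/60) = 0.31.

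| Difference between strata (points) | Power, s = 0.5 | Power, s = 0.3 |
|---|---|---|
| 0.275 | 23% | 21% |
| 0.40 | 36% | 33% |
| 0.55 | 55% | 49% |

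The difference detectable with 80% power at s = 0.5 is (1.645 + 0.842) × 0.31 = 0.77 points. That exceeds the whole assumed treatment effect of 0.55.

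**5. HbA1c: what the continuous baseline would add**

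Assumptions: baseline HbA1c is truncated normal on 7.0–9.5% (the range in Section 5.7), with mean 8.0–8.2 and SD 0.6–0.8 before truncation. After truncation the total SD B is 0.53–0.60 and the within-stratum SD W is 0.30–0.34. The slope b of change on baseline is 0.3–0.7 in size. The total SD of change, S, is 1.2 (SAP) or 1.0 (assumed).

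- Residual variance with the stratum only: S² − b²(B² − W²).
- Residual variance with the stratum and continuous baseline: S² − b²B².

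Lowest case (B = 0.53, W = 0.30, b = 0.3, S = 1.2): 1.4228 against 1.4147, SE ratio √1.0057 = 1.003.

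Highest case at the SAP's SD (B = 0.60, W = 0.34, b = 0.7, S = 1.2): 1.3202 against 1.2636, SE ratio √1.0448 = 1.022. Power for a 0.55-point interaction goes from 58.1% to 59.7%.

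The same case with S = 1.0: 0.8802 against 0.8236, SE ratio √1.0687 = 1.034. Power goes from 73.2% to 75.7%.

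Dropping continuous baseline HbA1c therefore inflates the SE by 0.3% to 3.4%, and restoring it adds at most about 2.5 percentage points of power.

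**The case against.** The strongest reply is that the HbA1c exclusion is a deliberate, stated choice. The model still adjusts for baseline HbA1c through the stratum and its interaction with visit, which is coarser but valid. There is also a reason for it. Section 5.2 requires LS means to be displayed. With both the stratum and the continuous baseline in the model, default LS means are evaluated at one common baseline HbA1c, which represents neither stratum. Treatment differences are unaffected, but the displayed stratum means would be extrapolations. This stands, and it makes the HbA1c half a matter of preference.

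On body weight, the reply is that the sentence names only baseline HbA1c, so a sensible programmer would carry baseline weight over from the general model. That is probably the intent, but the text does not say so. The separate model is set out in full and lists no covariate.

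Three stronger readings are tempting, and the SAP does not support them:

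- **That the omission biases the subgroup effects.** Treatment is randomised, so the within-stratum treatment contrasts are not biased by leaving out a baseline covariate.
- **That the omission explains the weak interaction test.** The low power in step 4 comes from the sample size and the split. Restoring the covariate barely moves it.
- **That the precision loss for HbA1c is substantial.** A baseline–change correlation of 0.5 would suggest an SE reduction of about 5%, but the SAP gives no such correlation. With SD 1.2 it implies a slope of 0.5 × 1.2/0.60 = 1.0 to 0.5 × 1.2/0.53 = 1.13, which is complete regression to the mean or more. Even a uniform baseline on 7.0–9.5% (SD 2.5/√12 = 0.72) needs a slope of 0.83.

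**Conclusion.** The body-weight point holds. The HbA1c-stratum model in Section 5.16 serves two outcomes but is worded for one, and taken literally it removes baseline weight from the weight analysis. The size depends entirely on a correlation that the SAP does not report; the figures in step 2 show the range for modest values.

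The HbA1c half is an optional refinement. Its small gain rests on assumed baseline distributions, slopes and, at the upper end, an SD of 1.0 instead of the SAP's 1.2.

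The stakes are low. The subgroups are exploratory and lie outside the graphical testing scheme, so no confirmatory conclusion depends on this model.

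**What to change.** In Section 5.16, restrict the exclusion sentence to the HbA1c outcome and add that, for body weight, baseline body weight remains a covariate in the HbA1c-stratum model, in line with Section 5.12.1. This is a wording change to the SAP; baseline weight is already collected and already used in the main weight model.

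Optionally, also keep continuous baseline HbA1c beside the stratum for the HbA1c outcome, as Section 5.15.2.2 does. If so, state that stratum LS means are evaluated at stratum-specific baseline HbA1c values. The cost is that extra specification. If the sponsor prefers the present HbA1c model, a one-line reason is enough.
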